#### **Analysis of pancreatic events**

- Pancreatitis
  - The number (%) of patients with events positively adjudicated as pancreatitis by the PSAC will be summarized by type: 1) acute pancreatitis, 2) acute on chronic pancreatitis, 3) chronic pancreatitis, 4) unknown pancreatitis.
  - All events sent to PSAC for adjudication for pancreatitis will be listed along with the adjudication outcome.
- Pancreatic neoplasm
  - All the events sent to PSAC for adjudication for pancreatic neoplasm will be listed along with the adjudication outcome including PSAC diagnosis, type of neoplasm (malignant, benign), cancer stage etc.

## **Analysis of major cardiovascular events**

The number (%) of patients with events adjudicated as major cardiovascular events by CAC will be summarized by treatment group. All events reported by the Investigators on the AE forms for cardiovascular events and the associated complementary forms (confirmed or not confirmed by CAC) will be listed along with the adjudication outcome.

## **Local tolerability at injection site**

Adverse events related to local intolerability at the injection site will be identified by searching the term “injection site” in the PTs coded from the Investigator reported terms. The number (%) of patients with related events will be summarized by treatment group, and sorted by decreasing incidence in the SAR425899 0.20 mg group.

All adverse events related to local intolerability at the injection site will be listed.

## ***Analysis of pre-treatment and post-treatment adverse events***

- All pre-treatment AEs by primary SOC and PT, showing the number (%) of patients with at least 1 pre-treatment AE, sorted by the internationally agreed SOC order and decreasing incidence of PTs within each SOC in the SAR425899 0.20 mg group.
- All post-treatment AEs by primary SOC and PT, showing the number (%) of patients with at least 1 post-treatment AE, sorted by the internationally agreed SOC order and decreasing incidence of PTs within each SOC in the SAR425899 0.20 mg group.

## ***Listings***

Supportive AE listings will be provided as appropriate for all AEs, SAEs and AEs leading to treatment discontinuation, TEAE leading to death, AESI, pancreatic events, major cardiovascular events, and adverse events related to local intolerability at the injection site. These listings will include at least the following information, sorted by treatment, patient identification, and onset date: treatment, patient identification, country, age, gender, race, BMI, primary SOC, PT, reported term, onset date, study day (relative day to the start date of treatment), AE duration, duration of exposure, intensity, corrective treatment, action taken with IMP, date of treatment discontinuation (if relevant), relationship to IMP/NIMP/study procedures, outcome, date of death (if any), seriousness, seriousness criteria, and AE status (“Pre” for a pre-treatment AE; “T” for a TEAE; and “Post” for a post-treatment AE).

### **2.4.5.3 Deaths**

The following summaries of deaths will be generated for the safety population.

- Number (%) of patients who died by study period (on-study, on-treatment, post-study)
- Deaths in nonrandomized patients or randomized but not treated patients
- TEAEs leading to death (death as an outcome on the eCRF AE page as reported by the investigator) by primary SOC, HLT, HLT, and PT, showing number (%) of patients, sorted by internationally agreed order of SOC and alphabetic order of HLT, HLT, and PT.

#### **2.4.5.4 Analyses of laboratory variables**

Laboratory parameters will be grouped and summarized by biological function as described in [Section 2.1.4.4](#).

The summary statistics (including number, mean, median, Q1, Q3, standard deviation, minimum and maximum) of all laboratory variables (central laboratory values and changes from baseline) will be calculated for each applicable visit or study assessment (screening, baseline, postbaseline time points, last on-treatment value) by treatment group.

The incidence of PCSAs (list provided in [Appendix A](#)) at any time during the treatment-emergent adverse event period will be summarized by biological function and treatment group whatever the baseline level and/or according to the following baseline status categories:

- Normal/Missing,
- Abnormal according to PCSA criterion or criteria.

For calcitonin and the albumin/creatinine ratio, no PCSA criterion is defined. Similar summaries using the pre-defined categories will be provided for the TEAE period. The pre-defined categories are, for calcitonin  $\leq$ ULN,  $>$ ULN - 20 ng/L,  $\geq$ 20 -  $<$ 50 ng/L, and  $\geq$ 50 ng/L (Note that ng/L is the standard international unit and is equivalent to pg/mL); and for albumin/creatinine ratio  $<$ 30  $\mu$ g/mg creatinine [Normal],  $\geq$ 30 to  $<$ 300  $\mu$ g/mg creatinine [Microalbuminuria], and  $\geq$ 300  $\mu$ g/mg creatinine [Macroalbuminuria].

For parameters for which no PCSA criteria are defined, similar table(s) using the normal range will be provided.

All measurements collected during the TEAE period, including values from unscheduled visits, will be considered for the PCSA summaries. These summaries will include patients in the safety population who have at least 1 assessment performed during the TEAE period. When a PCSA definition involves a change from baseline value, patients must also have a baseline value to be included in the summaries, and when required by the definition of the abnormality, patients must also have available laboratory normal ranges.

A listing of patients with at least 1 post-baseline PCSA (or out of normal range when no PCSA criterion is defined) will be provided and will display the entire patients' profile across time for all parameters belonging to the corresponding biological function. Individual data listings will include flags when applicable:

- Baseline values will be flagged "B".
- Normal laboratory ranges, available for most laboratory parameters, will be identified as ULN and LLN. Baseline, last on-treatment value, and individual data will be flagged "L" if the value is below the LLN and will be flagged "H" if it is above the ULN.
- Laboratory PCSA criteria will be used for the corresponding laboratory parameters. Values reaching a PCSA limit will be flagged (+, ++, -, or -- depending upon the direction and level of the abnormality). Flags for WBC and differential counts will be determined using data expressed in international units.

For parameters whose PCSA criteria are multiples of the ULN, the parameter's value will also be expressed as a multiple of the ULN in the individual data provided.

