8.1.1 SAR425899 or matching placebo (solution for injection)

- Pharmaceutical form: SAR425899 solution for injection or matching placebo are supplied as cartridges containing 3 mL solutions for injection containing:
 - For SAR425899: SAR425899 at a concentration of 0.5 mg/mL in sodium dihydrogen phosphate dihydrate, di-sodium hydrogen phosphate dodecahydrate, sodium chloride, m-cresol, HCL/NaOH and water for injection,
 - For SAR425899 placebo: sodium dihydrogen phosphate dihydrate, disodium hydrogen phosphate dodecahydrate, sodium chloride, m-cresol, HCL/NaOH and water for injection.
- Route and method of administration: SC injection using the pen-type injector (Tactipen®).
- Dose of IMP per administration:
 - For SAR425899 and matching placebo, patients will be randomized to following dose regimen :
 - Low dose: 1 step weekly dose increase (if no significant tolerability issues [example, nausea and vomiting] are observed): 0.06 mg ie, 12U – 0.12 mg ie, 24U (0.12mg ie, 24U for 25 weeks).
 - Mid dose: 2 step weekly dose increase (if no significant tolerability issues [example, nausea and vomiting] are observed): 0.06 mg ie, 12U – 0.12 mg ie, 24U – 0.16 mg ie, 32U (0.16 mg ie, 32U for 24 weeks).
 - High dose: 3 step weekly dose increase (if no significant tolerability issues [example, nausea and vomiting] are observed): 0.06 mg ie, 12U – 0.12 mg ie, 24U – 0.16 mg ie, 32U – 0.20 mg ie, 40U (0.20 mg ie, 40U for 23 weeks).
- Timing: doses of SAR425899 and placebo should be injected in the morning at the same time every day except on clinic visit days.
- On clinic visit days, SAR425899 and placebo injection time should be after blood tests/ECG measurement time in the morning and be coordinated with the meal test/PK sampling time.

If the target dose is not tolerated, the study treatment can be decreased. Another attempt for dose increase may take place within 4 weeks and before Week 8 of treatment. Then, if the patient cannot reach or tolerate the target dose, he/she remains at the lower dose. If he/she cannot tolerate the lower dose, end of treatment assessments are done. Then, the patient will be discontinued from IMP but continues in the study and is followed up according to the study procedures as specified in this protocol (except for the post-treatment follow-up), up to the scheduled date of study completion. After Week 8, if the dose is no longer tolerated, final on-treatment visit assessments are done and the patient is discontinued from the IMP.

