**Table 1 - Protocol amendment statistical changes**

Amendment Number	Date Approved	Rationale	Description of statistical changes
1	23-Jan-2017	
Increased urinary free-cortisol level was observed in animal studies of SAR425899 but the relevance of this finding to human is unclear. The Food and Drug Administration (FDA) requested to add the measurement of urinary free-cortisol and creatinine from 24h urines at baseline and end of treatment in order to assess the increase in urinary free-cortisol in humans which may suggest a potential effect of SAR425899 on the hypothalamic-pituitaryadrenal axis.
 
In phase I studies an increase of ketones bodies was observed for the SAR425899 high dose group (up to 0.18 mg) but not for placebo and the SAR425899 low dose group. In view of the currently requested administration of up to 0.20 mg of SAR425899 and the potential gastrointestinal side effects together with the simultaneous administration of metformin, the BfArM recommended to consider metabolic acidosis as an adverse event of special interest with an immediate notification in order to recognize this state very early in the study and to discontinue the administration of metformin when applicable.
 
Leptin and microRNA were initially considered as biomarkers of interest in this study. Leptin plasma concentrations are correlated with fat mass. MicroRNA is a surrogate biomarker for nonalcoholic steatohepatitis (NASH). Thus assessment of these two biomarkers was expected to provide information about SAR425899 effect on fat mass and NASH. However the sponsor decided to not measure these parameters anymore during this phase II study. For Leptin, it is not required for any modeling and is not recommended as a surrogate to test for differences in energy expenditure. Nevertheless Leptin and fat mass changes are planned to be assessed in a study dedicated to energy expenditure assessment. For MicroRNA, patients included in this study are not diagnosed for NASH and no liver biopsy is taken which could make the interpretation of microRNA results difficult. Nevertheless microRNA is planned to be assessed in a study dedicated to NASH.
	
To add urinary free-cortisol and creatinine measured in 24 hours urines at baseline and in Visit 12 (Week 26, End of treatment).
 
To add metabolic acidosis as a new adverse event of special interest as requested by the BfArM.
 
To remove Leptin and microRNA assessments

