**Table 2 - Statistical analysis plan statistical changes**

SAP version number	Date approved	Rationale	Description of statistical changes
1	This version	
Increased urinary free-cortisol level was observed in animal studies of SAR425899 but the relevance of this finding to human is unclear. The FDA requested to add the measurement of urinary free-cortisol and creatinine from 24h urines at baseline and end of treatment in order to assess the increase in urinary free-cortisol in humans which may suggest a potential effect of SAR425899 on the hypothalamic-pituitaryadrenal axis.
 
In phase I studies an increase of ketones bodies was observed for the SAR425899 high dose group (up to 0.18 mg) but not for placebo and the SAR425899 low dose group. In view of the currently requested administration of up to 0.20 mg of SAR425899 and the potential gastrointestinal side effects together with the simultaneous administration of metformin, the BfArM recommended to consider metabolic acidosis as an adverse event of special interest with an immediate notification in order to recognize this state very early in the study and to discontinue the administration of metformin when applicable.
 
Leptin and microRNA were initially considered as biomarkers of interest in this study. Leptin plasma concentrations are correlated with fat mass. MicroRNA is a surrogate biomarker for nonalcoholic steatohepatitis (NASH). Thus assessment of these two biomarkers was expected to provide information about SAR425899 effect on fat mass and NASH. However the sponsor decided to not measure these parameters anymore during this phase II study. For Leptin, it is not required for any modeling and is not recommended as a surrogate to test for differences in energy expenditure. Nevertheless Leptin and fat mass changes are planned to be assessed in a study dedicated to energy expenditure assessment. For MicroRNA, patients included in this study are not diagnosed for NASH and no liver biopsy is taken which could make the interpretation of microRNA results difficult. Nevertheless microRNA is planned to be assessed in a study dedicated to NASH.
 
Potentially an interim analysis for population PK and PK/PD will be performed for 60% completers, in order to have data for internal project planning purposes.
 
To add Amylase/lipase assessment in Visits 9 and 11 as requested by the BfArM.
 
To change the reference timepoint for blood sampling during the meal test from the end of the standardized meal to the start of the standardized meal and change the time period for the standardized meal consumption from 15 minutes to 10 minutes.
	
Urinary free-cortisol and creatinine measured in 24 hours urines, and the cortisol/creatinine ratio were added to the list of laboratory variables for statistical analyses.
 
Metabolic acidosis was added to the list of AESI parameters for statistical analyses.
 
Leptin and microRNA were removed from the list of pharmacodynamics biomarkers for statistical analyses.
 
An interim PK/PD analysis will be performed for 60% completers.
 
Visit 9 and 11 amylase/lipase assessments will be included in the analyses of amylase/lipase.
 
There will be no change to the planned by timepoint analyses on meal test related efficacy parameters due to the change, however, sensitivity analyses may be performed as necessary.

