#### **2.1.4.4 Laboratory safety variables**

Clinical laboratory data consists of blood analysis (including hematology and clinical chemistry, amylase, lipase, calcitonin) and urinalysis (albumin/creatinine ratio). Clinical laboratory values will be summarized in both standard international units and conventional units.

The laboratory data will be collected at designated visits (see study flowchart in [Appendix C](#). The following laboratory data will be measured at a central laboratory and used as safety endpoints:

- Hematology
  - Red blood cells, platelets: hemoglobin, hematocrit, red blood cells (erythrocytes) count, platelets count.
  - White blood cells: white blood cells count, and differential counts (neutrophils, lymphocytes, monocytes, basophils, and eosinophils).
- Clinical chemistry
  - Electrolytes: sodium, potassium, calcium, phosphorus.
  - Renal function: creatinine, calculated eGFR, cystatin C, uric acid.
  - Liver function: alanine aminotransferases (ALT), aspartate aminotransferases (AST), alkaline phosphatase (ALP), gamma-glutamyl transpeptidase (GGT), total bilirubin (and, in case of values above the normal range, differentiation in conjugated and non-conjugated bilirubin).
- Thyroid panel: Thyroid-stimulating hormone (TSH), Total Triiodothyronine (T3) and Free Thyroxine (FT4).
- Pancreatic enzymes: lipase, amylase.
- Serum calcitonin.
- Urine analysis: albumin/creatinine ratio.
- Urinary free-cortisol and creatinine based on 24-hour urine sample in some patients, 24-hr free-cortisol/creatinine ratio will be derived for these patients.

Lipid parameters (fasting): total cholesterol, triglycerides, LDL-C, and HDL-C are presented as efficacy parameters in [Section 2.1.3.2](#).

Other laboratory data not mentioned above (serology tests (hepatitis B antigen, hepatitis C antibodies), serum pregnancy test, serum follicle-stimulating hormone [FSH], and estradiol) will not be defined as safety endpoints (collected as per study flowchart in [Appendix C](#)).

Technical formulas are described in [Section 2.5.1](#).

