### **2.3.2 Safety population**

Safety analyses will be based on the safety population, defined as all randomized patients who receive at least 1 dose of IMP (regardless of the amount of treatment administered). Patients will be analyzed for safety analyses according to the treatment actually received. For a patient randomized to a SAR425899 treatment arm, the patient will be analyzed in the treatment he/she receives starting Week 8 visit (inclusive) when no adjustment of dose level is allowed. However, for a patient randomized to a SAR425899 treatment arm and discontinues the IMP before Week 8 visit, the patient will be analyzed in the SAR425899 treatment arm the patient is randomized to. If a patient is exposed to more than one dose level of SAR425899 since Week 8 visit or later, then the patient will be analyzed in the dose level administered on Week 8 visit or study day 56 if Week 8 visit is not available. If a patient is treated with both placebo and SAR425899 any time during the study, the patient will be analyzed in the SAR425899 treatment arm. Liraglutide patients will be included in the Liraglutide treatment arm regardless of dose amount patients receive.

In addition:

- Nonrandomized but treated patients will not be part of the safety population; however, their safety data will be presented separately;

- Randomized patients for whom it is unclear whether they took the IMP will be included in the safety population as randomized;
- Patients will be excluded from the safety population only if there is documented evidence (ie, all study dates recorded as no medication taken) that patients have not taken the study medication.

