### *General common rules*

All safety analyses will be performed on the safety population as defined in [Section 2.3.2](#), unless otherwise specified, using the following common rules:

- Safety data in patients who do not belong to the safety population (eg, exposed but not randomized) will be listed separately;
- The baseline value is defined as the last available value before the first injection of IMP.
- The PCSA values are defined as abnormal values considered medically important by the Sponsor according to predefined criteria/thresholds based on literature review and defined by the Sponsor for clinical laboratory tests, vital signs, and ECG (PCSA version dated May 2014 [[Appendix A](#)]).
- PCSA criteria will determine which patients had at least 1 PCSA during the TEAE period, taking into account all evaluations performed during the TEAE period, including unscheduled or repeated evaluations. The number of all such patients will be the numerator for the treatment-emergent PCSA percentage;
- The treatment-emergent PCSA denominator by group for a given parameter will be based on the number of patients assessed for that given parameter during the TEAE period by treatment group in the safety population;
- For laboratory parameters cited in the protocol as efficacy endpoints (including HbA1c and plasma glucose), PCSA summaries will not be provided. These parameters will be summarized in [Section 2.4.4](#);
- For quantitative safety parameters based on central laboratory/reading measurements, descriptive statistics will be used to summarize results and change from baseline values by visit and treatment group. Summaries will include the last on-treatment value (see [Section 2.4.5.4](#));
- The analysis of the safety variables will be essentially descriptive and no systematic testing is planned. Relative risks versus placebo and their 95% CIs may be provided, if relevant;
- Selected safety analyses will be summarized by age group (<50, ≥50 to <65, ≥65 to <75, ≥75 years of age), gender, race subgroups, and any pertinent subgroups as appropriate (see details in [Section 2.4.5.1](#) and [Section 2.4.5.2](#)).

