#### **2.4.5.7 24-hours Holter ECG**

The summary statistics (including number, mean, median, Q1, Q3, standard deviation, minimum and maximum) of all Holter ECG variables (24-hour average and night time average heart rate, and changes from baseline) will be calculated for each applicable visit or study assessment (screening, baseline, postbaseline time points, last on-treatment value) by treatment group. For parameters 24-hour average and night time average heart rate, mean changes from baseline with the corresponding standard error will be plotted over time (at same time points) in each treatment group.

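### FDA-requested 24-hour urinary free cortisol gets by-arm summaries only; a baseline-adjusted ratio to placebo with a 95% CI would be a cheap improvement

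*SAP*

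**What the plan says.** SAP Table 1 (section 1.5) records that urinary free cortisol rose in animal studies and that the FDA wanted 24-hour collections before the first dose and again when treatment finishes. The stated purpose is "in order to assess the increase in urinary free-cortisol in humans which may suggest a potential effect of SAR425899"; the system of interest is the hypothalamic-pituitary-adrenal axis. Table 2 (section 1.6) adds that cortisol, creatinine and "the cortisol/creatinine ratio were added to the list of laboratory variables for statistical analyses". The protocol flow chart schedules the collection for Visit 4 and Visit 12. SAP 2.1.4.4 lists the variable as "Urinary free-cortisol and creatinine based on 24-hour urine sample in some patients", without giving a number.

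The planned analysis is in SAP 2.4.5.4. Number, mean, median, quartiles, SD and range "of all laboratory variables (central laboratory values and changes from baseline) will be calculated for each applicable visit or study assessment", by treatment group. Incidence tables by abnormality criterion, or by normal range where no criterion exists, and listings follow. The general rules in SAP 2.4.5 state: "The analysis of the safety variables will be essentially descriptive and no systematic testing is planned". They also allow relative risks versus placebo with 95% CIs where relevant, but do not promise them.

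Laboratory data use the safety population. Under SAP 2.3.2, for a patient randomized to SAR425899, "the patient will be analyzed in the treatment he/she receives starting Week 8 visit (inclusive) when no adjustment of dose level is allowed". Protocol 8.1.1 explains how dose received can differ from dose assigned: "If the target dose is not tolerated, the study treatment can be decreased".

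**The concern.** The measurement was added to answer one question: does cortisol rise on SAR425899? That is a comparison with placebo, and the baseline needed to sharpen it is collected. The plan nevertheless leaves the reader to subtract one arm's arithmetic mean from another's. The result would not be adjusted for baseline, would have no planned interval, and would rest on at most 30 placebo patients. A geometric mean ratio, a natural scale if cortisol is right-skewed, cannot be recovered from arithmetic summaries.

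The SAP already contains the method. Section 2.4.9.1 plans a baseline-adjusted ANCOVA with 95% CIs versus placebo for the exploratory patient-reported outcomes. A safety measurement requested by a regulator gets less.

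What is at stake is how precisely and directly one safety question is answered. No efficacy conclusion or error rate is affected.

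**Working it through.** **The plan's own figure.** The documents give no power, SD or precision for cortisol. The arm sizes used below come from the HbA1c calculation (protocol 11.1), which reproduces. With SD 1.1, 60 v 30 patients and a difference of 0.7, SE = 1.1 × √(1/60 + 1/30) = 0.246 and 0.7/0.246 = 2.85. The noncentral t with 88 df gives 80.4% power, against the stated 80%.

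**Assumed inputs (not in the documents).** Log-scale SD s of 0.4 to 0.8, equal at baseline and Week 26; correlation r between the two of 0.3 to 0.7; 60% to 100% of patients with both samples.

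**Step 1: gain from baseline adjustment.** The planned table gives both Week 26 values and changes, so the fair comparator is the better of the two. With k = √(1/n1 + 1/n0):

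- ANCOVA: SE = s√(1−r²) × k
- Week 26 value alone: SE = s × k, so the ratio to ANCOVA is 1/√(1−r²)
- Change from baseline: SE = s√(2(1−r)) × k, so the ratio is √(2/(1+r))

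| r | Week 26 value / ANCOVA | Change / ANCOVA | Better of the two |
|---|---|---|---|
| 0.3 | 1.05 | 1.24 | 1.05 |
| 0.4 | 1.09 | 1.20 | 1.09 |
| 0.5 | 1.15 | 1.15 | 1.15 |
| 0.6 | 1.25 | 1.12 | 1.12 |
| 0.7 | 1.40 | 1.08 | 1.08 |

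The loss against the better summary is about 5% to 15%. The planned table is arithmetic, so these log-scale figures stand in for its precision and do not measure it exactly.

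**Step 2: expected interval.** The 95% CI is the estimate multiplied and divided by exp(t × SE). For one dose (60 v 30), k = 0.224 and t = 1.99. At s = 0.6 and r = 0.5, SE = 0.6 × 0.866 × 0.224 = 0.116, and the factor is exp(1.99 × 0.116) = 1.26. Either unadjusted comparison gives 1.31. Over the assumed ranges of s and r, the ANCOVA factors are:

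- one dose, all paired (60 v 30): 1.14 to 1.40
- one dose, 60% paired (36 v 18): 1.18 to 1.56
- all doses pooled (180 v 30): 1.12 to 1.35
- all doses pooled, 60% paired (108 v 18): 1.15 to 1.47

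**Step 3: effect of grouping by dose received.** Assume no drug effect. A share p of every arm does not tolerate the dose and has g times higher cortisol for other reasons. In the 0.16 and 0.20 mg arms that share steps down one level. Grouped by dose received, the log ratios to placebo are:

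- 0.12 mg: (2p/(1+p) − p) × ln g
- 0.16 mg: 0
- 0.20 mg: −p × ln g

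At p = 0.2 and g = 1.3 (ln g = 0.262) these are 0.0350, 0 and −0.0525, so the ratios are 1.04, 1.00 and 0.95. At p = 0.1 and g = 1.3 they are 1.02, 1.00 and 0.97. An extreme case (p = 0.3, g = 1.6) gives 1.08, 1.00 and 0.87. As randomized, all are 1.00, provided non-tolerators are equally likely to have samples in every arm.

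For the pooled contrast at p = 0.2 and g = 1.3, the groups hold 72, 60 and 48 patients. The weighted mean log ratio is (72 × 0.0350 + 60 × 0 − 48 × 0.0525)/180 = 0. Step-downs move patients only between SAR425899 doses, so the overall contrast with placebo does not change.

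**The case against.** The plan follows one stated policy. Safety is descriptive, and heart rate, which is named in a main secondary objective, is handled the same way: for the Holter variables, "mean changes from baseline with the corresponding standard error will be plotted over time" by arm and no model is fitted. Cortisol is in no listed objective. As the SAP records it, the FDA asked for the measurement, not for a modelled comparison, and the SAP added the variable and its ratio to the laboratory analyses. A reader can already set SAR425899 against pooled placebo by eye. All of this stands, and it is why the point is an improvement and not an error.

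Three stronger readings are tempting, and the documents do not support them.

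- A reader might infer a precision loss of up to 24%. That figure (r = 0.3) compares ANCOVA only with change from baseline. SAP 2.4.5.4 also gives Week 26 values, which at that correlation lose only 5%.
- A reader might infer that dose-received grouping distorts the answer on whether the drug raises cortisol. It does not touch the pooled contrast, apart from dispensing errors. At p of 10% to 20% and g = 1.3, the by-dose shifts of 2% to 5% lie well inside even the narrowest single-dose interval factor, 1.14.
- A reader might infer that grouping as randomized is therefore the unbiased choice. With a real dose-related rise, counting stepped-down patients at their assigned dose dilutes the high-dose signal, which is the less cautious direction for safety. Patients with both samples on treatment are a post-randomization subset under either grouping.

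SAP Appendix A (abnormality criteria) and Appendix B (summary of analyses) were not in the supplied text and might say more about cortisol.

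**Conclusion.** The point holds as a minor, low-cost improvement. In the supplied SAP text, the variable added to detect a cortisol rise has no committed baseline-adjusted comparison with placebo, although both samples are scheduled and the model is already used elsewhere in the plan. Under assumed correlations of 0.3 to 0.7, the better unadjusted log-scale comparison has an SE about 5% to 15% larger than ANCOVA. The larger practical gain is a prespecified ratio with an interval in place of a hand calculation. Grouping is a secondary matter for by-dose ratios only, and neither grouping can be called unbiased. All cortisol magnitudes rest on assumed SDs, correlations, sample counts and step-down patterns.

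**What to change.** In SAP 2.4.5.4 keep the planned summaries. For 24-hour urinary free cortisol and the cortisol/creatinine ratio, add an ANCOVA of the log Week 26 on-treatment value with treatment, the two randomization strata and log baseline. Report the geometric mean ratio to pooled placebo with a 95% CI for all SAR425899 doses together and for each dose, and the number per arm with both samples. Do no hypothesis test, which keeps to the descriptive policy. Show the by-dose ratios both as randomized and by dose received, without presenting either as unbiased.

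The cost is a few lines of SAP text and one extra table; no new data are needed. Intervals may be wide. The samples come from only some patients, and the earliest may lack a baseline, because enrolment began on 23 December 2016 and the measurement was added by the amendment of 23 January 2017. The estimate applies only to patients with both samples on treatment, so the planned last on-treatment summary should stay as the broader descriptive view.
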